5.2.7. Sum of Lesion Diameters

For lesions that are assessed as 'too small to measure', 5 mm will be imputed and used in the calculation of the sum of the lesion diameters.

5.2.8. Adequate Baseline Tumor Assessment

Adequate baseline is defined using the following criteria:

- All baseline assessments must be within 35 days prior to and including the date of first dose.
- All documented lesions must have non-missing assessments (i.e. non missing measurements for target lesions and non-missing lesions status at baseline for nontarget lesions).
- Measurable disease at baseline (see Section 5.2.5 for the definition of measurable disease)

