# SCHEDULE OF ACTIVITIES

The Schedule of Activities table provides an overview of the protocol visits and procedures. Refer to STUDY PROCEDURES and ASSESSMENTS sections of the protocol for detailed information on each procedure and assessment required for compliance with the protocol.

The Investigator may schedule visits (unplanned visits) in addition to those listed on the Schedule of Activities, in order to conduct evaluations or assessments required to protect the wellbeing of the participant.

Visit Identifier	Screening	Cycle 1 (28 days)	Visit on Day 1 of Every Cycle	End of Treatment	Follow-Up 
Visit Window	≤28 days	Day 1	±2 days	$\pm 7$ days	
Informed consent 	X	2			
Tumor history	Х				
Medical history	Х				
Physical examination and vital signs	Х	Х	Х	Х	
Body weight		Х	Х	Х	
ECOG performance status	Х	Х	Х	Х	
Contraception check  (as appropriate)		Х	Х	X	Х
Laboratory					
Hematology	Х	(X)	Х	Х	
Blood chemistry	Х	(X)	Х	Х	
Lipids	Х	(X)	Х	Х	
Pregnancy test 	Х	Х	Х	Х	Х
Cardiac Monitoring					
12-Lead ECG 	Х	(X)	X (every cycle up to Cycle 5)	Х	
Treatment					
Lorlatinib			Orally once daily, conti	nuously	
Tumor Assessments					
CT or MRI imaging 	Х		X (every 12 weeks $\pm 1$ week)	Х	
Other Clinical Assessmen					
Serious and non-serious AEs 	Х	Х	Х	X	Х
Concomitant medications and non-drug supportive interventions 	Х	Х	Х	Х	Х

(X): No need to repeat if assessment performed within 7 days prior to Cycle 1 Day 1.

Abbreviations: AE=adverse event; CAP=chest abdomen pelvis; CRF=case report form; CT=computed tomography; CTCAE=Common Terminology Criteria for Adverse Events; ECG=electrocardiogram; ECOG=Eastern Cooperative Oncology Group; MRI=magnetic resonance imaging; NCI=National Cancer Institute; QTc=QT interval corrected for heart rate; RECIST=Response Evaluation Criteria in Solid Tumor; SAE=serious adverse event.

- 1. Informed consent must be obtained prior to undergoing any study-specific procedures that are not considered standard of care.
- 2. Contraceptive check: participant may be contacted by phone to confirm contraception is still appropriate per the protocol.

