## 4.2. Exclusion Criteria

Participants presenting with any of the following will not be included in the study:

- Radiation therapy (except palliative to relieve bone pain) within 2 weeks of study enrollment. Palliative radiation (<10 fractions) must have been completed at least 48 hours prior to study enrollment. Stereotactic or small field brain irradiation must have completed at least 2 weeks prior to study enrollment. Whole brain radiation must have completed at least 4 weeks prior to study enrollment. Prior irradiation to >25% of the bone marrow.
- 2. Major surgery within 4 weeks prior to enrollment. Minor surgical procedures (eg, port insertion) are not excluded, but sufficient time should have passed for adequate wound healing.
- 3. Known prior or suspected severe hypersensitivity to study drug or any component in its formulation.
- 4. Active and clinically significant bacterial, fungal, or viral infection.
- 5. Clinically significant vascular (both arterial and venous) and non-vascular cardiac conditions (active or within 3 months prior to enrollment), which may include, but are not limited to:
  - a. Arterial disease such as cerebral vascular accident/stroke (including transient ischemic attack [TIA]), myocardial infarction, unstable angina;

- b. Venous diseases such as cerebral venous thrombosis, symptomatic pulmonary embolism;
- c. Non-vascular cardiac disease such as congestive heart failure (New York Heart Association Classification Class ≥II), second degree or third degree atrioventricular (AV) block (unless paced) or any AV block with PR interval >220 msec; or ongoing cardiac dysrhythmias of NCI CTCAE Grade ≥2, uncontrolled atrial fibrillation of any grade, bradycardia defined as <50 beats per minute (bpm) (unless participant is otherwise healthy such as long distance runners, etc.), machine read ECG with QT interval corrected for heart rate (QTc) >470 msec, or congenital long QT syndrome.
- 6. History or known presence of interstitial fibrosis, interstitial lung disease (ILD), pneumonitis, hypersensitivity pneumonitis, interstitial pneumonia, obliterative bronchiolitis, and pulmonary fibrosis.

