# 6. STUDY PROCEDURES

#### 6.1. Screening

All participants being considered for the study and eligible for screening must sign an informed consent for the study before completing any study-specific procedures. Participants will be screened within 28 days prior to first dosing of lorlatinib to confirm that they meet the eligibility criteria for the study. The required screening assessments are summarized in the Schedule of Activities and Section 7 Assessments.

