## 7. ASSESSMENTS

## 7.1. Antitumor Activity Assessments

Tumor assessments will include all known or suspected disease sites. Computed tomography (CT) or magnetic resonance imaging (MRI) scans of chest abdomen pelvis (CAP) and MRI of the brain will be performed at Screening. Gadolinium contrast enhanced MRI must be used for assessment of CNS lesions with contingent slices of 1 mm for lesions 5 mm to 10 mm in size, 5 mm for lesions greater than 10 mm. For all tumor assessments, the method of assessment that was used at Screening should be the same method used throughout the study. CT and MRI scans to be done at every 12 weeks  $\pm 1$  week till the end of treatment. Tumor assessment should be repeated at the end of treatment if more than 6 weeks have passed since the last evaluation. Moreover, radiological tumor assessments will be conducted whenever disease progression is suspected (eg, symptomatic deterioration).

Assessment of response will be made using RECIST version 1.1 (Appendix 3). Confirmation of response will be required at least 4 weeks after initial response is observed.

All participants' files and radiologic images must be available for source verification.

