#### Lesions with prior local treatment

• Tumor lesions situated in a previously irradiated area, or in an area subjected to other loco-regional therapy, are usually not considered measurable unless there has been demonstrated progression in the lesion.

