3.4. Baseline Variables

Start and end dates of study treatment:

The date of first dose (start date) of study treatment is the earliest date of non-zero dosing of the study drug.

The date of last dose of study treatment is the latest date of non-zero dosing of the study drug.

Definition of baseline:

No windowing will be applied when defining baseline, except as noted in Section 5.2.8 for tumor assessments. Any deviations from the protocol specified window will be documented as protocol deviations. A separate definition of adequate baseline will be provided for tumor assessment related antitumor activity endpoints.

For antitumor activity analyses and baseline characteristics associated with tumor assessments the last assessment prior to treatment start date will serve as the baseline assessment.

For safety (including laboratory, vital signs and Eastern Cooperative Oncology Group (ECOG) performance status) the last assessment performed on or prior to date of the first

dose of study treatment will serve as the baseline assessment. If there are no observations meeting these criteria, then baseline is considered missing.

Participants who start treatment and discontinue from the study on the same day may have two different sets of data collected on study day 1 (one during study and one in the End of Treatment (EOT) visit. Data reported at the EOT visit are not eligible for baseline selection.

Triplicate electrocardiograms (ECGs) are collected pre-dose; therefore, the baseline for each ECG measurement is the average of the latest pre-dose triplicate measurements. Unscheduled assessments will not be included in the calculation of the average.

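### Nothing requires the baseline brain MRI to follow radiotherapy permitted before first dose, so radiation shrinkage can be credited to lorlatinib, mainly in IC-ORR

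*SAP*

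**What the plan says.** **Baseline scan.** Protocol 6.1 sets the window: "Participants will be screened within 28 days prior to first dosing of lorlatinib". Protocol 7.1 adds that "MRI of the brain will be performed at Screening". For antitumor endpoints, SAP 3.4 selects the scan by date alone: "the last assessment prior to treatment start date will serve as the baseline assessment". SAP 5.2.8 then defines adequacy: "All baseline assessments must be within 35 days prior to and including the date of first dose", with complete lesion data and measurable disease. Under SAP 3.2.1 and 3.2.2 an inadequate baseline makes the participant a non-responder, so 5.2.8 determines whose shrinkage can count.

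**Radiotherapy before entry.** Protocol 4.2, item 1, says: "Stereotactic or small field brain irradiation must have completed at least 2 weeks prior to study enrollment". The limit for whole-brain radiation is 4 weeks before enrollment. Short-course palliative radiation, which the item excepts when given for bone pain, "must have been completed at least 48 hours prior to study enrollment".

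**Rules that touch irradiated lesions.** Protocol Appendix 3 says that lesions in a previously irradiated area "are usually not considered measurable unless there has been demonstrated progression in the lesion". SAP 5.2.3 recognizes new anticancer therapy only after the first lorlatinib dose, and radiotherapy only when recorded as curative. SAP 6.2.2 says that surgery or radiotherapy to extracranial lesions leaves IC-OR unchanged. It is silent on brain irradiation before first dose.

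**The concern.** The scan window runs back from first dose, while the radiotherapy limits run back from enrollment. They are set independently and nothing orders one after the other. A lesion can therefore be measured, irradiated, and then followed on lorlatinib against its size before irradiation. Shrinkage at the 12-week scan, if confirmed at least 4 weeks later, would be scored as lorlatinib response.

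The study has a single arm and investigator-read response, so no control group absorbs such an effect. For the response rates it acts in one direction, upward. It bears most on IC-ORR: participants with asymptomatic CNS metastases are eligible, the intracranial denominator is only a subset of about 100 treated participants, and brain irradiation acts directly on the lesions being scored.

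**Working it through.** The plan gives no figure on this point. Its only precision figure, the maximum standard error of an adverse event rate, reproduces as √(0.5 × 0.5 / 100) = 0.05, but plays no part here.

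**1. Length of the gap.** Inputs:
- Scan window W: 28 days (Protocol 6.1) or 35 days (SAP 5.2.8).
- Minimum interval m from end of radiotherapy to enrollment: 14 days (stereotactic or small-field brain), 28 days (whole brain), 2 days (palliative for bone pain), all from Protocol 4.2.
- Lag L from enrollment to first dose: not given, so taken as 0, 7 and 14 days.

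The longest time by which the baseline scan can precede the end of radiotherapy is max(0, W − m − L). Results in days, protocol window / SAP window:

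| Radiotherapy | m | L = 0 | L = 7 | L = 14 |
|---|---|---|---|---|
| Stereotactic or small-field brain | 14 | 14 / 21 | 7 / 14 | 0 / 7 |
| Whole brain | 28 | 0 / 7 | 0 / 0 | 0 / 0 |
| Palliative, bone pain | 2 | 26 / 33 | 19 / 26 | 12 / 19 |

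For stereotactic treatment at L = 0: 28 − 14 − 0 = 14 and 35 − 14 − 0 = 21. In practice: MRI on day -28, irradiation ending on day -14, enrollment and first dose together. No stated limit is broken, and the day -28 MRI is the baseline unless another scan follows.

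**2. The enrollment anchor.** SAP section 4 defines the enrolled set by signature of consent. On that reading, stereotactic treatment ends at least 14 days before consent, so any scan done after consent follows it. The gap then needs a scan taken before consent. The Schedule of Activities leaves room for that: "Informed consent must be obtained prior to undergoing any study-specific procedures that are not considered standard of care".

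**3. Do other rules close it?**
- *Appendix 3* deals with lesions already irradiated and says only what is usual. It does not clearly reach a lesion scanned first and irradiated afterwards. The SAP 5.2.5 definition of measurable disease does not mention irradiation.
- *SAP 5.2.3* starts at first dose, so earlier radiotherapy neither ends response assessment nor censors.
- *SAP 3.4* helps only if a later scan before first dose happens to exist.
- *Non-target lesions.* In Protocol Table 5, a participant with target lesions reaches PR through the target lesions even if non-target disease persists. A vanished non-target lesion only moves PR to CR. The exception is a participant whose only intracranial lesions are non-target: the measurable-disease criterion in SAP 5.2.8 is not stated to be intracranial, so disappearance of those lesions could be scored IC-CR.

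**4. Which endpoint.** Brain irradiation bears on IC-ORR, and on overall ORR where brain lesions are included. Palliative bone radiotherapy can affect only overall ORR. Even there, Appendix 3 makes blastic lesions non-measurable and admits lytic or mixed lesions only with a measurable soft-tissue component.

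**5. Size per participant.** The documents do not give the number with CNS metastases. Assuming 30 to 50, one misattributed responder adds 100/50 = 2.0 to 100/30 = 3.3 points to IC-ORR. With 100 treated, one adds 100/100 = 1.0 point to overall ORR.

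**The case against.** The strongest reply is that this is a narrow path. Much of it stands:

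- **35-day figures.** A reader might infer that sites can follow every rule and still have gaps of 21, 33 or 7 days. They cannot. Scans on days -29 to -35 fall outside protocol screening, and SAP 3.4 records departures from the protocol window as deviations. What remains is that SAP 5.2.8 still accepts such scans for analysis.
- **Whole-brain radiation.** Within the protocol window the overlap is 0.
- **Palliative radiation.** Its long overlap might be read as a threat to intracranial response. The exception is for bone pain, so it is not.
- **Lag and consent.** The 14 days require enrollment at first dose. On the consent reading, the case needs an MRI before both radiotherapy and consent, no later MRI, and dosing within 28 days of that MRI.
- **Investigator judgment.** Investigators may apply Appendix 3 and pass over a lesion they know was irradiated. That lowers the risk, but the wording does not oblige them to do so.
- **Importance.** These are descriptive secondary estimates in a safety study without hypothesis tests. A participant who would have responded anyway adds nothing to the bias.

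The reply does not remove the core case. Stereotactic or small-field brain irradiation after the baseline MRI is possible within the protocol's own window, and no analysis rule catches it.

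**Conclusion.** The point holds for scan order. The plan lets the baseline brain MRI precede permitted stereotactic or small-field brain irradiation by up to 14 days within the protocol window, and by up to 21 days if scans accepted only by the SAP are included. Both figures assume enrollment at first dose. Shrinkage from that irradiation can then be credited to lorlatinib.

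The direction is upward for IC-ORR and, less, for ORR. The effect on DoR and IC-DoR has no clear direction. The number of participants affected cannot be derived, so the documents support no estimate of total bias. The 2.0 to 3.3 points per misattributed responder rest on the assumed 30 to 50 participants with CNS metastases. The primary endpoint is untouched.

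**What to change.** Add to SAP 5.2.8, and apply in 6.2.1 and 6.2.2:

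- A lesion irradiated after the baseline scan and before first dose is not eligible as a target lesion. Its shrinkage or disappearance does not count towards CR or PR, or IC-CR or IC-PR.
- If all intracranial lesions were so treated, the participant is a non-responder for IC-ORR.
- Where a scan after the radiotherapy and before first dose exists, it serves as the baseline.

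The cost is a check of radiotherapy dates against scan dates and a slightly lower response rate. SAP 6.2.1 builds best overall response from the investigator's reported responses, so the check must be done before those responses are used. No extra scan is needed, and no eligibility, radiotherapy or dosing rule changes.

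The rule corrects scan order only. It does not remove shrinkage that continues after radiotherapy completed before the baseline scan, and the report should say so.

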3.2.2. Confirmed Intracranial Objective Response Rate (IC-ORR)

Intracranial OR based on investigator assessment is defined as IC-CR or IC-PR according to RECIST v1.1 from date of first dose until documented Intracranial Progressive Disease (IC-PD) or start of new anticancer therapy without regard to discontinuation from treatment. Both

IC-CR and IC-PR must be confirmed by repeat assessments performed no less than 4 weeks after the criteria for response are first met. Participants without IC-CR or IC-PR or with death prior to first post-baseline assessment, inadequate baseline assessment, new anticancer therapy started prior to first post-baseline assessment, and all post-baseline disease assessments missing will be considered as non-responders.

IC-ORR is defined as the percent of participants with intracranial response (ie, best overall intracranial response as confirmed CR or confirmed PR considering only intracranial lesions) relative to participants with CNS metastases at study entry.

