6.2.2. Confirmed IC-OR

Analysis set: Participants with CNS metastases based on Investigator Assessment

Analysis methodology:

The IC-OR will be summarized similar to OR (as described above in section 6.2.1), in Safety Population with CNS metastases based on investigator assessment. Surgery or radiotherapy of extracranial lesions will not affect the determination of IC-OR.

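### The SAP's only adequate-baseline rule is whole-body, so a purely extracranial baseline defect can turn a confirmed intracranial responder into a non-responder

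*SAP*

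**What the plan says.** SAP 3.4 (Baseline Variables) refers to Section 5.2.8 for tumor assessments and announces: "A separate definition of adequate baseline will be provided for tumor assessment related antitumor activity endpoints". SAP 5.2.8 then sets three criteria:

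- timing: "All baseline assessments must be within 35 days prior to and including the date of first dose";
- completeness: "All documented lesions must have non-missing assessments", meaning a measurement for each target lesion and a status for each non-target lesion;
- measurable disease at baseline, as defined in SAP 5.2.5.

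None of the three is split by site, and the SAP has no intracranial counterpart.

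SAP 3.2.2 defines intracranial response "considering only intracranial lesions", over a denominator of everyone with CNS metastases at entry. Its non-response rule lists "inadequate baseline assessment, new anticancer therapy started prior to first post-baseline assessment, and all post-baseline disease assessments missing will be considered as non-responders". SAP 6.2.2 adds: "The IC-OR will be summarized similar to OR", which brings in the matching rule from 6.2.1. Protocol 9.4 scores an inadequate baseline as non-response for antitumor analyses generally. The one extracranial exemption, in SAP 6.2.2 and 6.2.4, covers surgery and radiotherapy.

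**The concern.** The endpoint looks only at the brain, while the gate in front of it looks at the whole body. A body scan that is too old, or an unrecorded value for one extracranial lesion, says nothing about whether the brain lesions were properly measured at baseline or whether they shrank. If such a defect triggers the non-response rule, the participant stays in the IC-ORR denominator and is lost from the numerator. The participant also leaves the IC-DoR set, which SAP 6.2.4 restricts to confirmed intracranial responders. IC-ORR and IC-DoR are named secondary endpoints in a subgroup of a 100-participant study, so single participants are visible in the result.

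**Working it through.** **Step 1: which definition governs.** SAP 3.2.2 uses the term inadequate baseline assessment without defining it. SAP 3.4 says a definition for the tumor endpoints will follow, and 5.2.8 is the only one that does.

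**Step 2: trace a participant.** Suppose a participant with CNS metastases has a complete brain MRI on day -10 and a confirmed intracranial response.

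| Baseline defect | 5.2.8 criterion failed | Brain data affected? | Literal result under 3.2.2 |
|---|---|---|---|
| Body CT on day -36 | Timing (36 > 35) | No | Intracranial non-responder |
| One extracranial target lesion without a measurement, or one non-target lesion without a status | Completeness | No | Intracranial non-responder |

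Without the defect the same participant is a responder. The denominator is unchanged, so for these defects the error in IC-ORR has one direction only: down.

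**Step 3: how easily the triggers arise.** Protocol 6.1 sets screening within 28 days of first dose, and the SAP allows 35, so there are 35 − 28 = 7 days of slack. A timing failure needs a body scan more than 7 days outside the screening window. The completeness failure needs no timing deviation. The documents give no frequency for either.

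**Step 4: size per participant.** The documents do not state the number m with CNS metastases; 30 to 50 of 100 is assumed. One lost responder moves IC-ORR by 100/m points:

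- m = 30: 100/30 = 3.3
- m = 40: 100/40 = 2.5
- m = 50: 100/50 = 2.0

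**Step 5: expected bias.** Protocol 1.2 cites an intracranial response of 55.6% in 9 patients, which is 5/9. The exact (Clopper-Pearson) 95% interval for 5/9 is 21.2% to 86.3%, as printed there. Take p = 5/9 as an illustrative true rate. Let q be the share of the CNS set with an extracranial-only defect, assumed unrelated to response. Expected reported IC-ORR = p × (1 − q).

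| q (assumed) | Reported IC-ORR | Bias (points) |
|---|---|---|
| 2% | 55.6 × 0.98 = 54.4% | −1.1 |
| 5% | 55.6 × 0.95 = 52.8% | −2.8 |
| 10% | 55.6 × 0.90 = 50.0% | −5.6 |

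**Step 6: against the sampling error.** With m = 40 and the planned Wilson interval, 22/40 = 55.0% (39.8 to 69.3). One lost responder gives 21/40 = 52.5% (37.5 to 67.1), and two give 20/40 = 50.0% (35.2 to 64.8). The shift is small beside an interval about 30 points wide.

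**The case against.** The strongest reply is that the SAP does not clearly say this. Section 3.2.2 never cites 5.2.8 by number, its wording sits inside an intracranial definition, and 6.2.2 asks only for a similar analysis. A programmer could reasonably confine the baseline check to the brain. A reader might infer from 5.2.8 that the SAP unambiguously commits to scoring these participants as non-responders. The documents do not go that far: the link rests on a shared term and on SAP 3.4. What remains is that 5.2.8 is the only definition and nothing restricts it, so the literal reading is the natural one, and two programmers could derive different rates from the same data.

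The triggers are also narrow. Protocol 7.1 requires body and brain imaging at Screening, and Appendix 3 requires target lesions to be measured and recorded at baseline. Monitors may check CRF data against source (Protocol 10). This stands as an argument that cases will be few, not that the rule is right.

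A reader might also infer an expected bias of 3 to 6 points. That needs a defect rate of 5% to 10%, which the documents do not support. At 2% and m = 40 the expected loss is 40 × 0.02 × 0.556 = 0.4 responders. Moreover, the 55.6% comes from patients with a measurable brain lesion, whereas this denominator is everyone with CNS metastases.

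Finally, no hypothesis test or decision rule is set even for the primary objective, and any error in IC-ORR is in the conservative direction. Both points limit the consequence.

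**Conclusion.** The point holds as a minor correction. Followed literally, SAP 5.2.8 with 3.4, 3.2.2 and 6.2.2 lets a body scan more than 35 days before first dose, or one missing extracranial measurement or status, cancel a confirmed intracranial response. The IC-ORR error can only be downward. The documents do not fix the direction for IC-DoR; there the effect is loss of eligible participants.

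Each affected responder costs 2.0 to 3.3 points if 30 to 50 participants have CNS metastases. The rates of 54.4%, 52.8% and 50.0% are illustrations under assumed defect rates of 2%, 5% and 10%, independent of response, and are not forecasts. Cases are probably uncommon. The primary adverse-event endpoint is untouched.

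The point concerns the timing and completeness criteria only. It does not show that the measurable-disease criterion should be dropped for intracranial response. That criterion is also whole-body, since a target lesion in any site can satisfy it, but it raises a different question.

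**What to change.** Add to SAP 5.2.8, with cross-references from 3.2.2, 6.2.2 and 6.2.4:

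> For IC-OR and IC-DoR, the first two criteria (35-day window; non-missing lesion assessments) are applied only to brain imaging and documented intracranial lesions; extracranial scan dates or missing extracranial values do not make the intracranial baseline inadequate. The measurable-disease criterion is not changed by this sentence.

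The last sentence matters. Saying only that adequacy is judged on the brain would leave it unclear whether measurable disease is still required, which could change who can count as an intracranial responder.

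The cost is this short SAP addition and one derived flag from data already collected. No new data are needed. It should be settled before database release.
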